8.6.1.5 Adrulipase Return, Destruction, and Recall

Return of IMP:

- Unused, partially used bottles will be returned by the patient to the investigational site.
- At the end of the study, the Monitor or First Wave BioPharma will conduct a final reconciliation between delivered, dispensed, and used/unused IMPs.

Destruction of IMP:

- Unused, partially used bottles must *not* be destroyed at the Investigative Sites without written authorization from First Wave BioPharma.
- Unused, partially used, or empty bottles returned to the pharmacy will be destroyed at the Hospital Pharmacy or First Wave BioPharma's Drug Distributor only after IMP accountability forms have been fully and accurately completed and verified by the Monitor.
- If an on-site destruction is requested, then the investigational site must provide procedural documentation and obtain written authorization for destruction from First Wave BioPharma, which will be filed along with the certificate of destruction in the IMP section of the pharmacy site file.

Recall:

- If an IMP batch is suspected to be defective, then First Wave BioPharma will immediately inform the Investigator and the hospital pharmacist.
- The Monitor will coordinate with the investigative site staff for the return of the concerned batches as per the return procedure. Depending on the study status, new batches may be sent to the investigational site.

8.6.2 Nonabsorbable Dye Marker

The dye marker FD&C Blue #2, also named Indigo carmine or Indigotin, will be supplied in accordance with current Good Manufacturing Practices (cGMP).

8.6.2.1 *Shipment, Receipt, and Storage and Dispensing*

The dye makers must be stored in a secured limited-access area and maintained at controlled room temperature $\leq 25^{\circ}\text{C}$ and will not require temperature monitoring during shipment.

9 TIMING OF STUDY PROCEDURES

Patients will provide written informed consent before any study-related procedures are performed.

9.1 The study Schedule of Assessments for Part 1 and Part 2 are included in Section 3.Screening Period

Throughout the screening period, patients are to remain on their prestudy porcine PERT.

9.1.1 *Visit 1, D-42 to D-14: Screening Visit*

The following procedures will be performed at the Screening Visit (which may take place over more than one day):

- Obtain signed informed consent from the patient before any study-related assessments are made
- Collect relevant medical history, including concomitant illnesses/diseases, previous/concomitant medications, and record AEs
- Full physical exam
- Specific CF assessment including a pulmonary function test by spirometry to determine $\text{FEV1} > 30\%$ of predicted normal for age, sex, and height at screening
- Record body height and weight
- Record vital signs while sitting (blood pressure, pulse rate, breathing rate, and temperature)
- Assess for eligibility (against the inclusion and exclusion criteria)
- Record demographic data such as ethnic origin, date of birth, and sex
- Collect urine sample for urinalysis
- Perform a serum pregnancy test, if applicable
- Collect samples for hematology, clinical chemistry, PT/INR, activated partial thromboplastin time (aPTT)
- Patients will be required to fast for at least 8 hours before the collection of screening laboratory tests (insulin dependent diabetics may be excluded from fasting).
- Collect samples for fasting lipids

- Obtain a stool sample for fecal pancreatic elastase concentration in the selected central laboratory

9.1.2 *Visit 2, D-7 to D-21: Stool Collection in Controlled Supervised Facility*

In advance of Visit 2, patients will be contacted by telephone and instructed to:

- Refrain from alcohol consumption for 24 hours before the visit
- Bring their prestudy porcine PERT with them to the clinic

Patients will be admitted for a maximum of 7 days to a facility providing supervised confinement for collection of stools for determination of CFA, CNA, and stool weight. The timing of the previous visit (Visit 1) should be made with the aim of accommodating the patients' schedules for the supervised confinement. To accommodate patients' schedules for the supervised confinement, a +7-day visit window is permitted.

- Patients will undergo admission to a controlled supervised facility for stool collection to support the CFA and CNA assessment and weight. A +7-day visit window is allowed to accommodate investigative site staff and patients' schedules for the supervised confinement.
- After appearance of fecal stool dye markers has been measured, patients CFA and CNA will be measured under their prestudy dose of porcine PERT using standardized high-fat meals during the 3-day standardized diet. Additional detailed information provided in the study operations manual should be followed.
- The CFA calculation will be based on the measured fecal fat content in relation to ingested fat quantities during the 3-day stool collection period.

The stool collection and dietary procedures will be conducted as described in [Section 9.2.4.1.](#) (Instructions for Supervised Confinement).

The following procedures will be performed at Visit 2:

- Review Inclusion /Exclusion Criteria
- Begin 72-hour controlled diet
- Focused physical exam to evaluate gastrointestinal tract, heart, and lungs
- Record body height and weight
- Record vital signs while sitting (blood pressure, pulse rate, breathing rate, and temperature)
- Record any changes in AEs and concomitant medication
- Instruct/dispense study drug

- Assess and record malabsorption signs and symptoms
- Marker-to-marker stool collection and stool weight (central laboratory will weigh the stool that is collected)
- Collect a serum sample for circulating anti-adrulipase antibodies and adrulipase concentrations
- Record all fat, protein, and dose of study drug taken with every meal and snack during the confinement period
- Verify study drug count on the last day of confinement

At the end of the supervised confinement (once the second blue dye marker sample has been collected), patients will remain on their prestudy porcine pert treatment. Patients will be contacted once the CFA results are available and if the patient is eligible to participate in the study visit 3 will be scheduled.

9.2 Treatment Period (Visits 3, 4 (T), 5 (T), and 6)

9.2.1 *Visit 3 (Day 1): Adrulipase Dispensation Visit - Must Occur Within 21 Days of Visit 1*

During the treatment period, patients will be randomized to receive adrulipase. Visit 3 will take place if the patient is eligible to continue based on data obtained at the Screening visit. The following procedures will be performed:

- Review Inclusion /Exclusion Criteria
- Perform a urine pregnancy test (urine dip stick), if applicable
- Assess and record malabsorption signs and symptoms
- Record any changes in AEs and concomitant medication
- Begin dose of adrulipase (For Part 1 subjects, 1.2 g/day; for Part 2 subjects, 3.3 g/day) in-clinic (optional if patient plans to eat immediately after the visit)
- Instruct patients on use and dosing (including patients' specific dose-titration for Part 1 patients).
- Instruct/dispense study drug to patient

9.2.2 *Visit 4 (Telephone) (Part 1 Day 5 ±2 or Part 2 Day 3 ± 2) and Visit 5 (Telephone) (Part 1 Day 10 ± 2 or Part 2 Day 7 ± 2)*

The following procedures will be performed during a telephone visit:

- Record any changes in AEs and concomitant medication review.
- Assess and record malabsorption signs and symptoms
- Confirm patient scheduled date for Visit 6 (second stool collection in a controlled supervised facility) and remind patients to arrive in a fasted status.
- PI and/or site staff may contact patient more frequently to enable patient-specific dose optimization (for Part 1 patients) as required
- Patient will remain on their optimized dose of adrulipase till visit 6
- Patients will be instructed to bring their adrulipase (all bottles dispensed, including full, partial or empty bottles) and prestudy porcine PERT with them to their next in-clinic visit.

9.2.3 *Visit 6: Stool Collection in Controlled Supervised Facility* (Part 1 Day 16 + 5 or Part 2 Day 10+3)

Patients will be admitted for a maximum of 7 days to a facility providing supervised confinement for collection of stools for determination of CFA, CNA, and stool weight. The timing of the previous visits should be made with the aim of accommodating the patients' schedules for the supervised confinement. To accommodate patients' schedules for the supervised confinement, a ± 5 day visit window is permitted.

- On Day 16 + 5 days (Part 1) or Day 10 + 3 (Part 2) (Visit 6), patients will undergo admission to a controlled supervised facility for stool collection to support the CFA and CNA assessment and weight. A +5-day (Part 1) or +3-day (Part 2) visit window is allowed to accommodate investigative site staff and patients' schedules for the supervised confinement.
- After appearance of fecal stool dye markers has been measured, patients CFA and CNA will be measured under their dose of adrulipase using standardized high-fat meals during the 3-day standardized diet. Additional detailed information provided in the study operations manual should be followed.
- The CFA calculation will be based on the measured fecal fat content in relation to ingested fat quantities during the 3-day stool collection period.

After completion of the initial treatment period during the completion of V6, patients will be instructed to switch their study medication to their prestudy porcine PERT. The stool collection and dietary procedures will be conducted as described in [Section 9.2.4.1.](#) (Instructions for Supervised Confinement)

The following procedures will be performed at Visit 6:

- Begin 72-hour controlled diet

- Focused physical exam to evaluate gastrointestinal tract, heart, and lungs
- Record body height and weight
- Record vital signs while sitting (blood pressure, pulse rate, breathing rate, and temperature)
- Record any changes in AEs and concomitant medication
- Instruct/dispense study drug for confinement period
- Assess and record malabsorption signs and symptoms
- Marker-to-marker stool collection and stool weight (central laboratory will weigh the stool that is collected)
- Collect urine sample for urinalysis
- Perform a urine pregnancy test (urine dip stick), if applicable
- Collect samples for hematology, clinical chemistry, PT/INR, and aPTT
- Collect samples for fasting lipids after patients have been in a fasting status for at least 8 hours (insulin dependent diabetics may be excluded from fasting).
- Record all fat, protein, and dose of study drug taken with every meal and snack during the confinement period
- Verify study drug count on the last day of confinement
- Return adrulipase on the last day of confinement

At the end of the supervised confinement (once the second blue dye marker sample has been collected), patients will return to their prestudy porcine PERT dose.

9.2.4 *Visit 7: End-of-Study /Early Termination Visit (Part 1 Day 28 ± 2 or Part 2 Day 21 ± 2)*

Patients will return to the clinic for their End of Study visit approximately 1 week after their last dose of study drug. If patients do not complete Visit 6, an Early Termination visit will be held approximately 1 week after the last dose of study drug. The procedures scheduled for the End-of-Study visit are the same as those that should be conducted for the Early Termination visit. The following procedures will be performed at the End-of-Study/Early Termination Visit:

- Focused physical exam to evaluate gastrointestinal tract, heart, and lungs
- Record any changes in AEs and concomitant medication
- Assess and record malabsorption signs and symptoms
- Collect a serum sample for circulating anti-adrulipase antibodies and adrulipase concentrations

- Perform a urine pregnancy test (urine dip stick), if applicable

9.2.4.1 *Instructions for Supervised Confinement for V2 and V6*

Dosing must have occurred for at least 16 days (Part 1) or 10 days (Part 2) prior to the supervised confinements. Beginning at breakfast (the first meal) on Day 1 of the supervised confinement, patients will be placed on a 72-hour controlled diet, with ~25 g fat/meal and 12.5 g fat/snack for a total of 100 g fat/day (3 meals and 2 snacks per day) and a minimum of 1.5 to 2 g of protein per kg of body weight. Although it is preferred to have the patient consume exactly 100 g of fat per day, the fat excretion assay remains valid with a fat intake range within 15% of the goal (i.e., 85 to 115 g of fat per day). The nutritional planning and calculation of dietary fat and nitrogen (protein) intake will be conducted by a qualified dietitian at each site. The actual fat and nitrogen (protein) intake will be calculated from the recorded type and amount of food consumed. A central laboratory will calculate CFA, CNA based on dietary intake and the fat and nitrogen excreted in stool. Stool weight values will also be recorded.

An indicator marker (500 mg of Food, Drug, and Cosmetics [FD&C] Blue #2) will be provided as two 250-mg capsules. The first marker (consisting of two 250-mg capsules) will be given at the beginning of breakfast or first meal on Day 1 of the supervised confinement to mark the start of the controlled diet. The second marker (two 250-mg capsules) will be given at the beginning of breakfast or first meal on Day 4 to mark the end of the controlled diet. Stool collection for fecal fat and nitrogen assessments must begin after the first marker has passed (the first stool containing the first marker is discarded) and is completed when the second marker has passed (the first stool containing the second marker is collected). Patients must continue the supervised confinement until the second stool marker is passed. The controlled diet will be maintained until the patient takes the second marker. Although it is not part of the controlled diet, the breakfast or first meal consumed on Day 4 of the supervised confinement should mimic (as closely as possible) the breakfast or first meal consumed on Day 1 of the supervised confinement.

If the patient has not passed the first blue dye marker within 4 days after ingesting the first dye marker capsules, or within 2 days after ingesting the second dye marker capsules, then 5-10 mg of oral bisacodyl may be given. Bisacodyl is the only laxative that may be given during the marker-to-marker stool collection period. Note: Patients on a stable chronic osmotic laxative may continue this therapy during the marker-to-marker stool collection.

The supervised confinement may take place within an inpatient facility or within an alternative confinement setting. This will be discussed and approved on an individual case basis by First Wave BioPharma. The alternative confinement setting will require the supervision of trained study site staff to oversee the study procedures.

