Table 2: Schedule of Assessments Part 2

	SCREENING		ADRULIPASE TREATMENT			END OF	
	Consent and Initial Evaluations	CFA on PERT	Dispense	Telephone Visits		CFA on Adrulipase	STUDY/EARLY TERMINATION
Visit Number	1 ^a	2 ^b	3	4 (T) ^c	5 (T) ^c	6 ^b	7
Study Week	-6	-2	1	2	3	4	5
Study Days	-42	-14	1	3	7	10	21
Visit Window (days)	+7	±7	±2	±2	±2	+3	±2
Pre-Visit Instructions	X	X		X	X		
Supervised confinement		X				X	
Clinical Assessments							
Obtain informed consent	X						
Demographics	X						
Complete history and physical	X						
Focused physical exam ^d		X				X	X
Confirm CF diagnosis (Inclusion Criteria 4)	X						
Height/weight, vital signs (sitting)	X	X				X	
Inclusion/exclusion criteria review	X	X	X				
Concomitant medications	X	X	X	X	X	X	X
Adverse events	X	X	X	X	X	X	X

	SCREENING		ADRULIPASE TREATMENT				END OF
	Consent and Initial Evaluations	CFA on PERT	Dispense	Telephone Visits		CFA on Adrulipase	STUDY/EARLY TERMINATION
Visit Number	1 ^a	2 ^b	3	4 (T) ^c	5 (T) ^c	6 ^b	7
Study Week	-6	-2	1	2	3	4	5
Study Days	-42	-14	1	3	7	10	21
Visit Window (days)	+7	±7	±2	±2	±2	+3	±2
Confirm scheduled date for next supervised confinement visit	X				X		
Study Treatment							
Instruct regarding study drug adrulipase dosing			X			X	
Full study drug accountability at the end of confinement						X	
Return Adrulipase at the end of confinement						X	
Record fat and protein intake and study drug taken at all meals and snacks			X			X	
Efficacy Measures							
Malabsorption signs & symptoms		X	X	X	X	X	X
72-hour controlled diet record		X				X	

	SCREENING		ADRULIPASE TREATMENT				END OF
	Consent and Initial Evaluations	CFA on PERT	Dispense	Telephone Visits		CFA on Adrulipase	STUDY/EARLY TERMINATION
Visit Number	1 ^a	2 ^b	3	4 (T) ^c	5 (T) ^c	6 ^b	7
Study Week	-6	-2	1	2	3	4	5
Study Days	-42	-14	1	3	7	10	21
Visit Window (days)	+7	±7	±2	±2	±2	+3	±2
Marker-to-marker stool collection and stool weight ^f		X				X	
Laboratory Tests							
Urinalysis	X					X	
Pregnancy test (serum for V1 screening and urine dipstick for other visits) ^g	X		X			X	X
Hematology, clinical chemistry, PT/INR, and aPTT ^h	X					X	
Fasting ⁱ lipids (patient to come in fasting status) and pre-albumin	X					X	
Serum samples for anti-adrulipase lipase antibodies and adrulipase concentrations		X				X	X
Fecal pancreatic elastase ^j	X						
Diagnostic Test							
Spirometry	X						

	SCREENING		ADRULIPASE TREATMENT				END OF

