6.6.2 MS1819/16/01 Phase 2a Study with MS1819 in patients with EPI due to chronic pancreatitis or pancreatectomy

An open-label, dose escalation Phase 2a study (MS1819/16/01) was conducted to investigate the safety of escalating doses of MS1819 in 11 patients with EPI caused by chronic pancreatitis or pancreatectomy.

The primary objective of this study was to investigate the safety of escalating doses of MS1819 (280 mg/day, 560 mg/day, 1120 mg/day, and 2240 mg/day). Each dose was given over a two-

week period. A CFA was obtained at baseline after washout, and after each escalating dose period. Safety assessments included immunoallergic side effects, digestive symptoms, and clinical laboratory tests. The secondary objective of this study was to investigate the efficacy of MS1819 by assessment of CFA.

Eleven patients were enrolled into the study, and ten completed all doses. One patient withdrew during the 1120 mg/day dose level due to severe diarrhea. This was not assessed as related to study drug.

In the Intent-to-Treat population, mean CFA rose from a baseline of 46.1% to 62.4% at the highest dose ($p = 0.001$). A number of symptoms improved comparing the highest dose to baseline, including stool consistency ($p < 0.001$), number of bowel movements ($p = 0.006$), steatorrhea ($p = 0.008$), and abdominal pain ($p = 0.148$). The treatment was well tolerated, with only two SAEs reported. Only one SAE was considered by the investigator to be possibly related to study drug, which was a patient with mild, transient elevations of liver enzymes. The elevations were between 2 and 3 X upper limit of normal (ULN), and lasted for about two weeks, a period of time that the patient was no longer receiving study drug. The patient had no symptoms of liver disease.

6.6.3 *AZ-CF2001, A Phase 2, Open-Label, Multicentre, 2x2 Crossover Trial to assess the Safety and Efficacy of MS1819-SD in Patients with Exocrine Pancreatic Insufficiency due to Cystic Fibrosis*

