8.3.4 Removal of Patients from the Study

A patient may be withdrawn from the study at any time for any of the following reasons:

- Lost to follow-up
- Voluntary withdrawal of consent by the patient, for any reason, at any time
- Major protocol deviations that could compromise the interpretation of the study results
- Occurrence of an immunoallergic reaction
- Occurrence of an adverse reaction (i.e., an SAE related to IMP) that justifies the discontinuation of the IMP
- Pregnancy

The date of withdrawal and the reason for withdrawal must be fully documented in the case report form (CRF) and a short narrative description should be added in the patient's medical records.

If at the time of withdrawal, the patient has received the investigational study product (partially or totally), study staff should encourage the patient to complete the Early Termination Visit (Visit 7) for follow-up safety investigations. These patients will be included in the mITT efficacy and safety analyses.

If the reason for discontinuation is due to an AE, then the Investigator will seek to obtain follow-up information and to document the event until its resolution or stabilization. In any case, the Investigator will take all necessary measures to ensure the patient's safety and ensure the patient is treated in accordance with local standard of care.

If a patient is lost to follow-up, then the Investigator should make every effort to obtain maximum information on the reasons for the nonattendance to the visit and on the patient's state of health. All attempts will be documented in the patient's medical records.

Pregnancy

Patients will be instructed that known or suspected pregnancy occurring during the study, in patients or female partners of male patients, should be confirmed and immediately reported to

the Investigator. Any patient who becomes pregnant during the study must be promptly withdrawn from the study. Upon discontinuation from the study, only those procedures that would not expose the patient to undue risk will be performed. The Investigator should also be notified of pregnancy occurring during the study but confirmed after completion of the study. If a patient is subsequently found to be pregnant after inclusion in the study, any pregnancy will be followed to term, and the status of mother and child will be reported to First Wave BioPharma after delivery.

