8.5. Clinical Laboratory Evaluation

All summaries except for the shift tables will be presented overall and by dose. Subjects are classified by maximum dose of adrulipase received during the study.

Values at Screening (Visit 1) and at 3 weeks post first dose, as described in Section 3, for laboratory parameters for hematology, clinical chemistry, and urinalysis will be summarized for the safety population using descriptive statistics.

Shift tables based on classification of values with respect to the reference range (low, normal, high) will be summarized for the safety population for critical clinical chemistry and hematology laboratory tests.

Post-baseline elevations in alanine aminotransferase (≥ 3 times the upper limit of normal [ULN]), aspartate aminotransferase (≥ 3 times ULN), total bilirubin (≥ 1.5 times ULN) will be summarized at Screening and at 3 Weeks Post First Dose. Hematology, clinical chemistry, hepatic monitoring, urinalysis, lipids, and pregnancy results will be presented in data listings for subjects in the safety population.

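### No hematology, chemistry or coagulation panel is scheduled at Visit 7/Early Termination, so a patient who stops before the Visit 6 samples has no scheduled post-dose safety panel

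*Protocol*

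**What the plan says.** - **Schedules (Protocol section 3, Tables 1 and 2; SAP 11.2).** The row "Hematology, clinical chemistry, PT/INR, and aPTT" is marked at Visit 1 and Visit 6 and nowhere else. Urinalysis and fasting lipids follow the same pattern. Visits 4 and 5 are telephone contacts, so nothing is sampled there.
- **Visit 6 (Protocol 9.2.3).** The list includes "Collect samples for hematology, clinical chemistry, PT/INR, and aPTT". It does not say on which day of a confinement of up to 7 days the blood is drawn. Section 9.2.2 tells sites to "remind patients to arrive in a fasted status", which suggests admission but does not fix it. Patients stay on adrulipase until the second dye marker has been collected.
- **Visit 7 (Protocol 9.2.4).** This is the End-of-Study visit and also the visit for patients who do not complete Visit 6: "The procedures scheduled for the End-of-Study visit are the same as those that should be conducted for the Early Termination visit". The list has a focused examination, AE and medication review, malabsorption symptoms, a urine pregnancy test and one blood item: "Collect a serum sample for circulating anti-adrulipase antibodies and adrulipase concentrations".
- **Withdrawals (Protocol 8.3.4).** For a patient who has taken study drug, "study staff should encourage the patient to complete the Early Termination Visit (Visit 7) for follow-up safety investigations".
- **Analysis (SAP 8.5).** Laboratory summaries use "Values at Screening (Visit 1) and at 3 weeks post first dose". The summary of ALT, AST and bilirubin elevations uses the same two time points.

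**The concern.** Safety laboratory values are a named safety endpoint (Protocol 8.2.3), yet each patient has only one scheduled chance to contribute a post-dose value. A patient who leaves before that chance contributes nothing to the post-dose laboratory tables, even after attending the visit that 8.3.4 provides for safety follow-up.

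Three features of the plan make the gap harder to excuse:

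- Protocol 10.1.1 does not count a laboratory abnormality as an AE if it has no clinical manifestation, needs no intervention and does not stop or delay drug. AE collection therefore cannot stand in for a panel.
- The hepatic monitoring rules in Protocol 10.7 work from ALT, AST and bilirubin values. No scheduled sample supplies these between screening and Visit 6, or after Visit 6.
- Protocol 6.7 says the Part 2 dose has not been used in prior studies.

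The SAP takes dropout seriously for efficacy, with best- and worst-case summaries of the CFA responder rate (SAP 9.2.4). It has no counterpart for laboratory data.

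**Working it through.** The plan states no figure on this point, so there is none to reproduce. The check compares the schedules and then sizes the gap.

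**1. Scheduled post-dose panels per patient**

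| Patient | Visit 6 | Visit 7/ET | Total |
|---|---|---|---|
| Reaches Visit 6 sampling | 1 | 0 | 1 |
| Dosed, stops before Visit 6 sampling | 0 | 0 | 0 |

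The protocol tables, the visit lists in 9.2.3 and 9.2.4, and the SAP schedule agree on this panel. Protocol 10.2 also refers to End-of-Therapy assessments for patients withdrawing because of an AE, but no schedule or visit list defines them.

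**2. Expected number of patients with no post-dose panel**

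Inputs: about 12 patients (Protocol 8.3.1); 5 stops during MS1819 among 41 enrolled in OPTION (6.6.3); 2 stops on MS1819 in the crossover phase among 44 enrolled in OPTION 2 (6.6.4). Six patients were already enrolled in Part 1 when version 2.0 was written (6.7). If the total stays near 12, about 12 − 6 = 6 remain for Part 2.

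Expected number = n × p; chance of at least one = 1 − (1 − p)^n.

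| Rate p | n = 12: expected | n = 12: P(≥1) | n = 6: expected | n = 6: P(≥1) |
|---|---|---|---|---|
| 2/44 = 0.045 | 0.55 | 0.43 | 0.27 | 0.24 |
| 5/41 = 0.122 | 1.46 | 0.79 | 0.73 | 0.54 |

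Counting the OPTION 2 extension stop and pooling gives (5 + 3)/(41 + 44) = 8/85, or 1.13 of 12, which lies inside the range.

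If no patient shows a given laboratory event, the one-sided 95% upper limit on its rate is 1 − 0.05^(1/n): 22.1% with 12 panels, 23.8% with 11 and 25.9% with 10. Losing one or two panels widens an already wide limit slightly. The main loss is the missing patients themselves, not precision.

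**3. Part 2 dosing after the last panel, if blood is drawn at admission**

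Dosing before admission must be at least 10 days (Table 2 note b; 9.2.4.1). Admission may be as late as Day 13 (Day 10 + 3), which is 12 elapsed days. Dosing after admission lasts at least the 3-day controlled diet and at most the 7-day confinement.

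Share after the panel = days after / (days before + days after):

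- 10 days before: 3/13 = 23% to 7/17 = 41%.
- 12 days before: 3/15 = 20% to 7/19 = 37%.

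The range is about 20–41%. A later draw within the confinement would lower it.

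**4. Effect of a Visit 7 panel**

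Every dosed patient who attends would have at least one post-dose panel, and completers would have two. On nominal days the second falls 28 − 16 = 12 days (Part 1) or 21 − 10 = 11 days (Part 2) after Visit 6 admission.

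**The case against.** The strongest reply is that this is a deliberate economy in a descriptive pilot of about 12 patients treated for two or three weeks. The three earlier CF studies reported unremarkable laboratory values (Protocol 6.6.3 to 6.6.5). No AEs had been reported when six patients were enrolled, five of them dosed at 2.4 g/day (6.7). Other routes also exist: Visit 6 may be held early in special circumstances (8.1), AEs that lead to discontinuation are followed to resolution or stabilization (8.3.4), and unscheduled hepatic tests are allowed (Tables 1 and 2, note h).

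This limits the importance of the point but does not remove it. An early Visit 6 needs discussion with the sponsor, AE follow-up needs an AE, and the hepatic tests are optional and meant for increases already found. The primary endpoint is unaffected.

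A reader might also infer more than the documents support:

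- **That early stoppers give no laboratory data at all.** Visit 7 collects antibodies and drug concentration, which 8.2.3 lists among the laboratory results. Only the safety panel is absent.
- **That early stoppers are the patients most likely to have a safety problem.** Section 6.6.3 attributes the OPTION stops on MS1819 mainly to symptoms of pancreatic insufficiency.
- **That this schedule would have missed the liver-enzyme SAE of the chronic pancreatitis study.** Section 6.6.2 says the rise "lasted for about two weeks, a period of time that the patient was no longer receiving study drug", but not when it was first detected. At 2 to 3 times ULN it is also below the 3-times threshold for ALT and AST in SAP 8.5, so a Visit 7 value would have shown it in summaries and listings, not in that elevation count.
- **That the three-week label in SAP 8.5 is part of this defect.** The SAP was written against protocol version 1.0 (SAP section 2). Its fit to Part 2 is a separate matter.

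**Conclusion.** The gap is real. The safety panel is scheduled once after the first dose, at Visit 6. A dosed patient who stops before that sample has no scheduled post-dose panel, and no patient has one after dosing ends. Laboratory changes in these windows are not scheduled to be detected; it does not follow that they would certainly be missed.

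The size is modest: about 0.5 to 1.5 of 12 patients, or 0.3 to 0.7 if the amendment reaches only about six Part 2 patients. This assumes that stopping rates from earlier formulations carry over, that enrolled patients are a fair denominator, and that every stop precedes Visit 6 sampling. The 20–41% share of Part 2 dosing after the last panel further assumes an admission draw, which the protocol does not fix.

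The change is worth making because it is cheap and completes a named safety endpoint, not because the documents show a particular hazard.

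**What to change.** **Protocol.** Add hematology and clinical chemistry, including ALT, AST and bilirubin, to Visit 7/Early Termination in Tables 1 and 2 and in the 9.2.4 list. Use the blood draw already scheduled there. At a minimum, require the panel for patients who stop before Visit 6 sampling.

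**SAP 8.5 and 11.2.** Mark the panel at Visit 7 in the schedule. Summarise and list the Visit 7/Early Termination values as their own time point, since they are taken about a week off drug, and include them in the summary of post-baseline ALT, AST and bilirubin elevations. State how many dosed patients have any post-dose panel.

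**Cost.** Up to about 12 extra central-laboratory panels and a short amendment to both documents. No new visit or venepuncture is needed.

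**Limit.** A panel about one week after the last dose would still miss changes that resolve within that week.
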